8.2 General Considerations

Data collected in this study will be presented using summary tables and patient data listings. Continuous variables will be summarized using descriptive statistics, specifically the mean, median, standard deviation (SD), minimum, and maximum. Categorical variables will be summarized by frequencies and percentages.

The statistical and analytical plans presented below summarize the more complete plans to be detailed in the statistical analysis plan (SAP). A change to the data analysis methods described in the protocol will require a protocol amendment only if it alters a principal feature of the protocol. The SAP will be finalized prior to database lock. Any changes to the methods described in the final SAP will be described and justified in the clinical study report.

8.3 Demographics, Baseline Characteristics, and Concomitant Medications

Demographic data, medical history, concomitant disease, and concomitant medication will be summarized by cohort and overall. To determine whether the criteria for study conduct are met, corresponding tables and listings will be provided. These will include a description of patients who did not meet the eligibility criteria, an assessment of protocol violations, study drug accountability, and other data that may impact the general conduct of the study.

Baseline characteristics will be summarized for the safety population. Patients who died or withdrew before treatment started or do not complete the required safety observations will be described and evaluated separately.

8.4 Treatment Compliance

Treatment administration will be summarized by cohort including dose administration, dose modifications or delays, cumulative dose, average dose, number of infusions, and the duration of therapy.

8.5 Analyses of Tumor Response

Patients will be classified according to their best overall tumor response (complete response [CR], partial response [PR], stable disease [SD], or progressive disease [PD]). Frequencies, proportions, and exact 95% CI of patients, when appropriate, stratified by their best overall tumor response will be calculated. Patients with a best overall tumor response of CR or PR with duration of at least 4 weeks (28 days) will be further classified as having an objective tumor response. Listing of patients with an objective tumor response will be presented.

Duration of response will be calculated as the number of days from the first documentation of overall response (CR or PR) to the first documentation of disease progression or death, whichever comes first. Patients who are alive and progression-free at the time of data analysis will be censored at the time of their last assessment for tumor response.

Duration of stable disease will be calculated from Cycle 1, Day 1.

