2.5 Secondary Endpoints

- PK parameters
- The incidence of AEs, clinical laboratory abnormalities, retinal findings, and ECG abnormalities
- Objective response per RECIST v1.1
- Duration of response per RECIST v1.1
- Levels of immune cell infiltrate in pre-treatment and on-treatment tumor biopsy samples

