3.2 Procedures

Patients will undergo safety evaluations (DLTs and other AEs, vital signs, ECGs, clinical laboratory tests), determination of ECOG performance status [PS], and physical and ophthalmologic examinations. Additionally, blood samples will be collected for PK analyses and for exploratory PD assessment in all patients. For all patients enrolled in Part 2, biopsy at the primary tumor site or metastatic site is mandatory, as feasible, at Screening (at least 24 hours

prior to Cycle 1 Day 1 dosing) and at **either** Day 15 (within 7 days prior to Cycle 1 Day 15 and at least 24 hours prior to dosing) **or** at Day 29 (within 7 days prior to Cycle 2 Day 1 and at least 24 hours prior to dosing). Feasibility at each timepoint will be assessed by the Investigator and should include a consideration of patient safety.

Tumor assessments will be performed at Screening (within 4 weeks prior to first dose), then every 6 weeks from the first dose, for 24 weeks, and every 12 weeks thereafter. Once an initial complete response (CR) or partial response (PR) is noted, confirmatory scans must be performed 4–6 weeks later. A tumor assessment should also be performed at the End-of-Study visit unless already performed within the previous 6 weeks or if tumor progression was previously determined. Response will be evaluated using RECIST v1.1. Subsequent tumor assessments will be performed using the same technique used to evaluate baseline tumor measurements. It is assumed that tumor assessments will be performed by CT unless clinical circumstances warrant the use of another methodology, in which case prior written approval must be obtained from the Sponsor.

Safety will be assessed by monitoring AEs and changes in physical examinations (including oral and ophthalmologic assessments), weight, vital signs, 12-lead ECGs, and laboratory measurements. Assessment of AEs will follow the guidelines provided in the National Cancer Institute (NCI) Common Toxicity Criteria for Adverse Events (CTCAE), version 4.03. Blood samples will also be drawn at scheduled time points during the study for determination of drug plasma concentration, and anti-drug antibodies (ADAs) (i.e., antibody response to FPA144).

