6.1 Tumor Response Parameters

Tumor assessments will be performed at Screening (within 28 days prior to first dose), then every 6 weeks from the first dose, for 24 weeks, and then every 12 weeks thereafter. Tumor assessments should be completed within 1 week prior to start of the dose when re-imaging is scheduled. All patients should have tumor response parameters assessed at the EOT visit unless a tumor assessment has been performed within the previous 6 weeks.

Response will be evaluated using RECIST v1.1 for measurable disease (*required for Part 2*). A response (complete or partial) to treatment must be confirmed 4–6 weeks later. Subsequent tumor assessments will be performed using the same physical, biomarker, or radiological parameter(s) used to measure the tumor at baseline.

Progressive disease is defined as the appearance of one or more of the following as described in RECIST v1.1 ([Eisenhauer 2009](#)):

- For patients with measurable disease, at least a 20% increase in the sum of diameters of target lesions, taking as reference the smallest sum on study (this includes the baseline sum if that is the smallest on study). In addition to the relative increase of 20%, the sum must also demonstrate an absolute increase of at least 5 mm.
- Unequivocal progression of currently or previously non-measurable lesions
- The appearance of one or more new lesions
- Development of clinical signs or symptoms which, in the opinion of the Investigator, indicate clinically significant disease progression

Note: Tumor assessments performed as part of the patient's standard of care within 28 days (4 weeks) of the first dose of FPA144 do not need to be repeated during screening.

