8.10 Determination of Sample Size

Three patients per dose group, with a sample size increase to 6 in the case of DLT, is generally accepted as adequate to determine the safety of escalating doses of novel oncologic drugs. If a DLT is observed in 1 of 3 patients, then 3 additional patients will be enrolled at that same dose level. Dose escalation will continue until 2 of 3–6 patients treated at a dose level experience a DLT. The maximum tolerated dose (MTD) is defined as the maximum dose at which < 33% of patients experience a DLT during Cycle 1. After the MTD is determined, additional gastric cancer patients may be recruited at that dose level to further characterize the safety, PK, pharmacodynamics, and preliminary efficacy of FPA144.

In Part 1B, up to 30 patients with gastric cancer with or without FGFR2b overexpression, in the presence or absence of *FGFR2* amplification may be enrolled to explore preliminary long-term safety and PK.

In each of the Part 2 gastric cancer cohorts (Cohorts A, C, D, and E), approximately 30 gastric cancer patients with ranges of FGFR2b overexpression scores (IHC 3+ \geq 10%; IHC 0; IHC 2+ \geq

10% tumor membrane staining **and/or** IHC 3+ < 10%; IHC 1+ **and/or** IHC 2+ < 10%) will be enrolled and treated to further characterize safety and preliminary efficacy. For each cohort, a response rate of $\geq 20\%$ would be considered clinically meaningful. To ensure adequate efficacy, an interim analysis may be performed (with the assumption that a response rate of $\leq 5\%$ would be of no interest in the first stage). Assuming a significance level of 5% and 80% power (Table 5), the required sample size is 29 evaluable patients per cohort. The Sponsor may choose to suspend enrollment if no confirmed response (CR or PR) is observed after the first 10 evaluable patients have either received at least 4 cycles of therapy or have had disease progression, as it is unlikely the response rate would be 20% or more. If a full cohort of 30 patients is enrolled for a group, the precision of the 95% confidence interval for the response rate is within 18%.

Table 6: Parameters of Simon’s 2-stage Design

Targeted Response Rate	Response Rate of No Interest	Overall Sample Size	Sample Size at Stage I	Responses to go to Stage II	Number of Overall Responses
20%	5%	29	10	≥ 1	≥ 4

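### The 28-day duration rule for objective response in Section 8.5 does not require a second scan showing CR or PR, so it does not match the confirmation rule in Sections 6.1 and 8.10

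*Combined protocol and SAP*

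**What the plan says.** Section 8.5 first classifies patients by best overall response. It then takes those with "CR or PR with duration of at least 4 weeks (28 days) will be further classified as having an objective tumor response". Duration of response is defined in the next paragraph as the "number of days from the first documentation of overall response (CR or PR) to the first documentation of disease progression or death", whichever is earlier. Patients alive and progression-free "will be censored at the time of their last assessment for tumor response". Section 8.5 does not mention confirmation or a second assessment and does not refer to Section 6.1.

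Other sections do require confirmation:

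- Section 6.1: "A response (complete or partial) to treatment must be confirmed 4–6 weeks later".
- Section 3.2, repeated in the tumor-scan footnote of Appendix 1: after a first CR or PR, "confirmatory scans must be performed 4–6 weeks later".
- Section 8.10: the sponsor may suspend enrollment if "no confirmed response (CR or PR) is observed" in the first 10 evaluable patients.

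The secondary endpoint in Section 2.5 is "Objective response per RECIST v1.1". Section 8.7 also cites RECIST v1.1 for response and its duration. Neither section states whether confirmation is needed. Table 6 speaks only of responses, at both stages.

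**The concern.** The 28-day condition looks like a stand-in for confirmation, because 28 days is the lower end of the 4–6 week window. But duration as 8.5 defines it ends only at progression or death. It does not end when a response is lost to stable disease, and it can reach 28 days with no second response on record. The rule can therefore count patients whom Section 6.1 would not.

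Two secondary objectives depend on this definition: the objective response rate (ORR) and duration of response. If the 8.5 class is what gets reported, ORR could be higher than the confirmed rate. It is also unclear whether the CR and PR patients in the duration summary of Section 8.7 are confirmed responders only, and whether the two response counts in Table 6 use the same definition as the stage 1 text.

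**Working it through.** **1. The plan's own figure.** Table 6 gives 10 then 29 patients, at least 1 response to continue, at least 4 overall, with rates of 5% (no interest) and 20% (target). The chance of meeting both conditions at true rate p is the sum over x = 1 to 10 of P(X = x) × P(Y ≥ 4 − x), with X ~ Bin(10, p) and Y ~ Bin(19, p).

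- p = 0.05: 0.0468, within the stated 5%.
- p = 0.20: 0.801, matching the stated 80%.

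The design reproduces. The open question is what counts as a response, not the design arithmetic.

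**2. Timing of the confirmatory scan.** Four to six weeks is 4 × 7 = 28 to 6 × 7 = 42 days after first CR or PR. For a patient who reaches that scan without earlier progression:

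- Progression on the scan: duration is 28 to 42 days, so the 28-day rule is met.
- Stable disease on the scan: this is not progression, so duration runs on or is censored on day 28 or later, and the rule is met. Section 6.1 requires a 20% and 5 mm increase over the smallest sum for target-lesion progression, so some regrowth is possible without ending duration.

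An on-schedule confirmatory scan therefore cannot fail the 28-day condition, whatever it shows.

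**3. Example sequences.** Days are counted from first dose, with a first PR at week 6 (day 42).

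| Course after PR at day 42 | Duration under 8.5 | Meets 8.5? | Second CR/PR? |
|---|---|---|---|
| SD at day 70, PD at week 18 (day 126) | 126 − 42 = 84 | Yes | No |
| PD at week 12 (day 84) | 84 − 42 = 42 | Yes | No |
| PD at day 70 | 70 − 42 = 28 | Yes | No |
| SD at day 70, then censored | 70 − 42 = 28 | Yes | No |
| No later scan, death at day 72 | 72 − 42 = 30 | Yes | No |
| No later scan, censored | 42 − 42 = 0 | No | No |

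Section 6.1 also counts as progression the "Development of clinical signs or symptoms which, in the opinion of the Investigator, indicate clinically significant disease progression". Clinical progression without a scan on or after day 28 of the response therefore behaves like the death row. The rule excludes only progression, death or a last assessment before day 28.

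**4. Size per patient.** One extra counted response shifts the rate by 1/n.

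- n = 20 (Cohort A in Section 4.1): 1/20 = 5.0 points.
- n = 30 (statistical part of the synopsis, which looks superseded): 1/30 = 3.3 points.

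For illustration, with exact (Clopper–Pearson) 95% intervals:

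- 3/20 = 15.0% (3.2–37.9%) becomes 4/20 = 20.0% (5.7–43.7%).
- 5/30 = 16.7% (5.6–34.7%) becomes 6/30 = 20.0% (7.7–38.6%).

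The per-patient shift is the same at any count. These denominators are planned enrollment; the Efficacy-Evaluable Population in Section 8.1.3 may be smaller.

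**The case against.** The best reply is that Section 6.1 is general and mandatory, and 8.5 does not set it aside. Best overall response could already mean a response confirmed under 6.1, with 28 days as a further condition, and then nothing conflicts. That reading is possible and may be what was intended. But 8.5 does not state it, and a second CR or PR at least 4 weeks after the first would already give 28 days, which makes the duration clause redundant.

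A second reply is that Sections 8 and 8.2 leave detail to a separate SAP to be finalized before database lock. That would answer a missing detail. Here a rule is stated, and read literally it gives a different count from 6.1.

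A third reply stands in part. In 8.5 the proportions and exact intervals are tied to best overall response; the 28-day class is tied explicitly only to a listing. Section 8.7 reports an overall response rate per RECIST v1.1 without naming that class. An effect on the reported ORR is therefore an inference that depends on which class is used.

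A reader might also infer that the two-stage design loses its error control. The documents do not support that. They give no share of responses that fail confirmation, Table 6 does not say which kind of response it counts, the stage 1 stop is optional, and Section 8.7 makes efficacy descriptive. Nor does crossing 20% in the illustrations reverse a decision: 20% is a target rate, Table 6 asks for 4 of 29 (13.8%), and the intervals overlap almost entirely.

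**Conclusion.** Wrong as written. The 28-day condition in 8.5 does not deliver the confirmation that Section 6.1 requires and that the stage 1 rule in 8.10 assumes. This rests on the literal text of 8.5 and on confirmatory scans being done in the 4–6 week window.

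The consequence for ORR is conditional: if the 8.5 class is the one reported, each unconfirmed response counted adds 5.0 points in a cohort of 20, or 3.3 in 30. The documents give no frequency for such cases, so no expected bias can be stated, and no claim of type I error inflation is made. The unclear population for the duration-of-response summary does not depend on that condition.

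**What to change.** In 8.5 and the SAP, replace the 28-day duration condition with: *CR or PR confirmed by a second assessment showing CR or PR, as required by Section 6.1 (not less than 4 weeks after the first).* State how a confirmatory scan later than the 6-week window is classified, so that 8.5 and 6.1 agree.

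Use this one definition for the ORR in 8.7, for both response counts in Table 6 and for entry to the duration-of-response analysis. Keep counting duration from the first documented CR or PR. List unconfirmed responses separately.

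The cost is a short text change in 8.5, with matching SAP text, before database lock. No new scans are needed, because Section 3.2 already requires the confirmatory scan. The downside is that the reported ORR may be slightly lower.

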8.6 Safety Analyses

Safety analyses will be performed separately within both parts of the study and for all patients combined. Data from all patients that receive any portion of at least 1 dose of FPA144 will be included in the safety analyses. AEs, clinical laboratory information, vital signs, ECOG performance status, body weight, ECGs, results of ophthalmology/retinal exams, and concomitant medications/procedures will be tabulated and summarized.

AEs will be summarized overall and with separate summaries for serious AEs, AEs leading to discontinuation, AEs leading to death, and NCI CTCAE Version 4.03 Grade 3 or higher AEs.

Body weight and vital signs will be summarized descriptively (N, mean, standard deviation, median, minimum, and maximum). ECOG will be summarized categorically and descriptively.

Shift tables displaying patient counts and percentages classified by baseline grade and maximum grade on treatment will be provided for laboratory data by cohort and overall. A marked laboratory change is defined as a shift from a baseline Grade 0 to Grade 3 (non-hematologic) or Grade 4 (hematologic) on treatment, or a shift from a baseline Grade 1 to Grade 4 on treatment. The number and percentage of patients with marked laboratory changes will be tabulated by cohort and overall.

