2.4 Primary Study Endpoints

- The incidence of Grade 3 and Grade 4 adverse events (AEs) and clinical laboratory abnormalities defined as dose-limiting toxicities (DLTs) (*Part 1 only*)
- The incidence of AEs and clinical laboratory abnormalities (*Parts 1B and 2 only*)

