4.2 Inclusion Criteria for Study Participation

Patients enrolling into Part 1(A and B) or Part 2 must meet *all* of the following inclusion criteria:

1. Understand and sign an Institutional Review Board/Independent Ethics Committee-approved informed consent form prior to any study-specific evaluation
2. Life expectancy of at least 3 months
3. ECOG performance status of 0 to 1
4. Age ≥ 18 years at the time the informed consent form is signed except for the patients in Taiwan, where the patient's age must be ≥ 20 at the time the informed consent form is signed
5. In sexually-active patients (i.e., females of childbearing potential, who have not undergone menopause as defined by 12 consecutive months of amenorrhea or had a permanent sterilization procedure and males, who have not had a permanent sterilization procedure), willingness to use 2 effective methods of contraception, of which one must be a physical barrier method (condom, diaphragm, or cervical/vault cap) until 6 months after the last dose of FPA144. Other effective forms of contraception are permanent sterilization (hysterectomy and/or bilateral oophorectomy, or bilateral tubal ligation with surgery, or vasectomy) at least 6 months prior to Screening. Female patients of childbearing potential must be on stable oral contraceptive therapy or intrauterine or implant device for at least 90 days prior to the study, or abstain from sexual intercourse as a way of living
6. Adequate hematological and biological function, confirmed by the following laboratory values:
 - a) Bone marrow function
 - ♦ $ANC \geq 1.5 \times 10^9/L$
 - ♦ Platelets $> 100 \times 10^9/L$
 - ♦ Hemoglobin ≥ 9 g/dL
 - b) Hepatic function
 - ♦ AST and ALT ≤ 3 x upper limit of normal (ULN); if liver metastases, then ≤ 5 x ULN
 - ♦ Bilirubin ≤ 1.5 x ULN
 - c) Renal function
 - ♦ Serum creatinine ≤ 1.5 x ULN
7. Tumor tissue, must be available for determination of FGFR2b overexpression (*optional for Part 1A patients*)

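### As worded, the marked-laboratory-change rule counts a non-hematologic Grade 1 to 4 shift but not the larger 0 to 4 shift, and it has no provision for tests that start at Grade 2 or 3

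*Combined protocol and SAP*

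**What the plan says.** Section 8.6 (Safety Analyses) plans two laboratory outputs. The first is a set of shift tables, with patients "classified by baseline grade and maximum grade on treatment will be provided for laboratory data by cohort and overall". The second is a summary rate: "The number and percentage of patients with marked laboratory changes will be tabulated by cohort and overall".

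The definition behind that rate has two limbs. The first is "a shift from a baseline Grade 0 to Grade 3 (non-hematologic) or Grade 4 (hematologic) on treatment". The second is "or a shift from a baseline Grade 1 to Grade 4 on treatment", with no distinction between laboratory classes. Neither limb mentions a baseline of Grade 2 or 3.

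Earlier in the same section, the adverse event summaries include "NCI CTCAE Version 4.03 Grade 3 or higher AEs", so the authors wrote an open-ended grade there and not in the laboratory rule.

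Two other places bear on the point. Section 2.4 lists "The incidence of AEs and clinical laboratory abnormalities" as a primary endpoint for Parts 1B and 2. Section 4.2, criterion 6, admits patients with raised transaminases, and "if liver metastases, then ≤ 5 x ULN".

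**The concern.** A summary of severe laboratory worsening should not drop a patient because the worsening was larger. Yet for a non-hematologic test the written rule counts a patient who goes from 0 to 3, counts one who goes from 1 to 4, and omits one who goes from 0 to 4.

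There is a second gap. If a test is already Grade 2 or 3 at baseline, no worsening to Grade 4 on that test can qualify. Such baselines are plausible here. Besides the transaminase allowance, Table 5 schedules tests for which criterion 6 sets no numeric limit, including alkaline phosphatase, sodium, potassium, calcium, albumin, phosphate and lymphocytes. Exclusion criterion 6 caps only acute effects of previous treatment at Grade 1. It does not cap abnormalities caused by the cancer.

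What is at stake is a reported safety percentage in small cohorts, and the chance that two programmers derive different counts from the same data.

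**Working it through.** The plan gives no figure for this rule, so there is nothing to reproduce. The check is an enumeration.

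**Inputs**, all from Section 8.6:
- Limb 1: baseline 0 to Grade 3 (non-hematologic) or to Grade 4 (hematologic).
- Limb 2: baseline 1 to Grade 4, either class.
- Classification by maximum on-treatment grade. The text states this for the shift tables. I assume it carries over to the definition two sentences later.

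**Method.** List every worsening that ends at Grade 3 or 4, from baseline Grades 0 to 3. Apply the rule twice: literally (maximum grade equals the named grade) and generously (maximum grade at least the named grade). For hematologic tests the two readings agree, because the named grade is already 4.

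| Baseline to maximum | Non-hematologic, literal | Non-hematologic, at least | Hematologic, either reading |
|---|---|---|---|
| 0 to 3 | counted | counted | not counted |
| 0 to 4 | **not counted** | counted | counted |
| 1 to 3 | not counted | not counted | not counted |
| 1 to 4 | counted | counted | counted |
| 2 to 3 | not counted | not counted | not counted |
| 2 to 4 | **not counted** | **not counted** | **not counted** |
| 3 to 4 | **not counted** | **not counted** | **not counted** |

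**Worsening to Grade 4.** There are 4 baseline grades × 2 classes = 8 cells.
- Literal: non-hematologic misses 3 of 4 (0 to 4, 2 to 4, 3 to 4) and hematologic misses 2 of 4 (2 to 4, 3 to 4). Total missed: 3 + 2 = 5 of 8.
- At least: non-hematologic misses 2 of 4 and hematologic misses 2 of 4. Total missed: 2 + 2 = 4 of 8.

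**Monotonicity.** Under the literal reading, for non-hematologic tests, 0 to 3 (three grades) and 1 to 4 (three grades) count, while 0 to 4 (four grades) does not. Under the generous reading this anomaly disappears.

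**What one omitted patient does to the rate.** Section 4.1 plans about 20 patients in Cohort A and up to 30 in Cohort F. One patient is 1/20 = 5 percentage points or 1/30 = 3.3 percentage points.

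These are counts of kinds of shift, not of patients. The documents do not say how many patients start at Grade 2 or 3 on any test, or how often a 0 to 4 shift occurs.

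**The case against.** The strongest defence is that the rule has a sensible intended meaning. Read *to Grade x* as reaching at least Grade x, and every named shift fits one threshold: a rise of three or more grades which, for hematology, must end at Grade 4. That rule is monotone. It explains why 1 to 3 is left out, and a baseline of Grade 2 or 3 cannot rise by three grades. The plan does not state this reading, but it is coherent. It follows that omitting 1 to 3 is a choice of convention, and that omitting baseline Grades 2 and 3 may be deliberate. It does not remove the wording problem, because the written rule lacks the open-ended phrasing that the same section uses for adverse events.

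The other outputs also limit the harm. The shift tables show every cell with counts and percentages. Laboratory results judged clinically significant go to the adverse event page and so reach the Grade 3 or higher summary, although Section 6.2.1.4 keeps those judged not clinically significant off that page.

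Section 8 announces a separate, more detailed SAP, to be finalized before database lock. It may settle the matter, but no other definition appears in the documents supplied.

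Four stronger conclusions might be drawn, and the documents do not support them:
- *The worst laboratory toxicities drop out of the rate.* Only some do. Hematologic 0 to 4 and 1 to 4 in both classes are expressly counted.
- *A patient with a Grade 2 baseline can never be counted.* Grades attach to tests. The same patient can still qualify on another test.
- *Patients admitted with transaminases up to 5 x ULN start at Grade 2.* The documents give no CTCAE laboratory cut-offs, so this cannot be confirmed from them.
- *The primary endpoint is misreported.* Section 2.4 does not define a laboratory abnormality as a marked change.

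**Conclusion.** The point holds as a defect of definition with a limited effect. Taken literally, and assuming classification by maximum grade, the non-hematologic rule is not monotone and can understate the marked-change rate. Independently of that reading, four of the eight kinds of worsening to Grade 4, all starting from Grade 2 or 3, are outside the rate without the plan saying whether this is intended.

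The size in patients cannot be derived and may be small: Section 1.7 reports no drug-related Grade 4 adverse event among 53 treated patients at the October 2016 cut-off. The effect stops at the marked-change number and percentage. The shift tables are unaffected, and none of the DLT definition, the dose modification guidelines or the sample size refers to this rate.

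**What to change.** In Section 8.6, or in the SAP before database lock:

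1. Change the first limb to read *Grade 0 to Grade 3 or higher (non-hematologic)*, leaving Grade 4 for hematologic tests, and say that the grade compared is the maximum on-treatment grade. This alone takes the uncounted kinds of Grade 4 worsening from 5 of 8 to 4 of 8 and restores monotonicity across the shifts from baseline Grades 0 and 1.
2. For baseline Grades 2 and 3, choose one option and state it. Either count any worsening to Grade 4, which brings the uncounted kinds to 0 of 8, or say that these shifts are intentionally excluded and shown only in the shift tables.

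Whether 1 to 3 counts as marked is a convention and need not change. A general rule of a two-grade rise would not be a full substitute, since it still leaves out 3 to 4.

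The cost is a sentence or two of text and a small programming change, with no new data or procedures. The reported rate may be slightly higher.
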